In summary, there is a pressing need to address AUDs during medical-surgical hospital stays, but prior work has not found support for existing strategies during this critical time period. We propose to help medical-surgical inpatients with AUDs understand the benefits of reducing or abstaining from drinking, and of different types of AUD help, and to initiate and engage with the type of care decided upon. The 2010 Affordable Care Act included provisions to foster adoption of decision aids and governmental support for their expansion. As required by the VHA Blueprint for Excellence that every research proposal clearly states how it will benefit Veterans and society, we anticipate that **DO-MoST will increase AUD-positive medical-surgical inpatients' utilization of evidence-based AUD help, improve AUD and medical outcomes, decrease use of acute care services, and thereby decrease societal harms and costs due to untreated AUDs.**

**A.7 Preliminary Studies.** The research team has a longstanding history of high-impact research on VHA addictions treatment and mutual-help use and on Veterans' help-related decision-making. Most relevant to the current proposal, the PIs completed a randomized trial (HSR&D IAC 09-055) of a MI intervention (in-person session, followed by weekly phone calls for 3 months) versus UC with psychiatry inpatients diagnosed with dual mental health and substance use disorders, to increase post-discharge use of specialty addiction treatment to improve outcomes. Of patients in the MI condition, 93% participated in the TM component of the intervention. Preliminary findings are that, at 1-year follow-up, compared to patients in UC (controlling for baseline drinking), patients in the MI condition reported significantly fewer drinking days in the past 90 days, and a lower percentage of days on which they drank. In addition, the number of consecutive days of abstinence was higher, and the number of consecutive drinking days was lower, for the MI group. These results suggest that telephone-based MI is a feasible, practical method of achieving clinically-meaningful improvements in alcohol-related outcomes among VHA dually diagnosed psychiatry inpatients. The 1-year follow-up rate exceeded 80%, consistent with our other projects (e.g., HSR&D IAC 09-047, [name], PI).

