### B.3 Aim 2: RCT of Drinking Options: Motivate, Shared Decisions, Telemonitor (DO-MoST) vs Usual Care (UC)

B.3.1 Power analysis. Based on previous research using MI or SDM approaches with inpatients to improve addiction treatment rates and outcomes, we expect to observe at least a medium effect size (.50) between the UC and DO-MoST groups in AUD help initiation and duration and alcohol use outcomes, e.g., percent of heavy drinking days, an FDA-recommended outcome, on which differences should be clinically meaningful. (For example, among treated AUD patients, the mean percent of heavy drinking days in the past 90 days decreased from 66% at baseline to 17% at 4-month follow-up.) We expect a smaller effect size in endpoint rehospitalization rates. We are planning to recruit a total sample of 156 patients (78 in each condition), which accounts for expected attrition. The sample will be stratified by site such that 78 patients will be recruited from VA Palo Alto, and 78 from VA Ann Arbor; at each site, 39 patients will enter each of the 2 conditions (UC or DO-MoST). These two sites were selected for this project because they have a high volume of medical-surgical inpatients with AUD (B.3.3) and differ geographically, and the two HSR&D COINs and PIs have a strong record of productive collaboration. In our recent joint project, rates of recruitment and follow-up were similar between sites.

B.3.2. Study population. Demographic characteristics of Veterans at the two sites are quite similar to those of Veteran medical-surgical inpatients nationwide. We expect that about 94% of participants will be male, and their mean age will be 60 years old (24% <50, 27% 50-64, 41% 65-79, 7% >79 years old). At Palo Alto, about 76% will be White, 9% Black, and 16% Hispanic; at Ann Arbor, about 86% will be white, 11% Black, and 2% Hispanic. Nationally, Veterans are mainly White (82%), with 12% Black, and 7% Hispanic.

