Research assistants, blinded to patients' condition assignment, will collect self-report data by telephone at 3 months, which will be upon completion of the intervention for the group in the DO-MoST condition, and then 6 and 12 months post-baseline. We will use an intent-to-treat design and so will follow patients who do not complete the intervention. Six months is a necessary follow-up point because most (60%-80%) patients treated for AUDs who relapse do so within this interval. Twelve months is a necessary follow-up point because the 6 months preceding that time point continue to be of high risk for relapse. Follow-up assessments will be conducted by telephone because patients may not reside in close geographical proximity to the Palo Alto or Ann Arbor VA. As noted (A.7), we have successfully used telephone interviews to collect follow-up data in HSR&D studies with inpatients. Follow-up interviews will take approximately one hour each. Patients will have the option of completing the interview in shorter sessions, with breaks, due to scheduling needs or fatigue.

We will measure patients' drinking and help preferences using the same measure with the Decision Coach at baseline. We will use the AUDIT-C, DSM 5 for alcohol diagnoses, TLFB, and SF-12 to measure substance use and medical status at follow-ups, supplemented by portions of the ASI. The TLFB (covering the period since the prior interview at each follow-up) will assess the same primary alcohol outcomes (abstinence, percent of drinking days, of heavy drinking days) and other substance use indices assessed at baseline. The ASI will provide recent (past 30 days) alcohol and drug use composite scores. The TLFB and ASI are valid and reliable when given by telephone. We will be able to compute dichotomous scores regarding abstinence from alcohol, drugs, and both alcohol and drugs over the assessed periods. The SF-12 will yield the primary outcome reflecting overall physical health status.

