**B.3.12 Examine mechanisms (reasons DO-MoST is effective).** Alcohol help initiation and engagement will be examined as mediators between condition and outcomes. We will conduct a series of regression models (controlling for covariates, e.g., baseline value of the dependent variable) that correspond to a hypothesized causal sequence among (1) DO-MoST, (2) alcohol help utilization, and (3) better alcohol and medical outcomes. First, the dummy variable representing DO-MoST is the independent variable and the dependent variable is the outcome (e.g., abstinence, percent of heavy drinking days). In the second regression, DO-MoST is the independent variable and the dependent variable is the potential mediator (e.g., duration of alcohol outpatient help). In the third regression the potential mediator is the independent variable and the dependent variable is the outcome. If the coefficient for DO-MoST or potential mediator is significant in all cases, we will proceed. In the final regression, DO-MoST is entered simultaneously with the utilization variable as predictors of the outcome. If the coefficient for utilization is significant and the coefficient for DO-MoST on the outcome is reduced, then we will conclude that a mediating effect of utilization is supported, and evaluate whether the indirect effect of DO-MoST on the outcome via treatment is significant.

We will also determine if increases in treatment utilization associated with DO-MoST are mediated by the mechanisms of reduced decisional conflict and increased motivation, commitment, and self-efficacy. We will conduct a series of regression models that correspond to a hypothesized causal sequence among (1) DO-MoST (vs. UC), (2) the potential mechanisms, and (3) use of alcohol treatment, and control for covariates. Analyses will use the same general linear model approach described in the previous paragraph. We will conduct regression analyses (covariates controlled) to examine associations of DO-MoST dose (number of phone sessions completed) with patients' outcomes at follow-ups, using methods (e.g., instrumental variables) to account for possible problems associated with endogeneity. We will explore whether less intensive (e.g., 3-session) doses of DO-MoST are as effective as the full, 6-session dose.

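### The mechanism analysis yields an indirect-effect estimate only if every significance step passes; reporting it with an interval in every case would be a cheap improvement in completeness, not in power

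*Combined protocol and SAP*

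**What the plan says.** B.3.12 describes a causal-steps procedure. Three regressions are fitted: outcome on condition, mediator on condition, and outcome on mediator. Then: "If the coefficient for DO-MoST or potential mediator is significant in all cases, we will proceed". A joint regression follows. "If the coefficient for utilization is significant and the coefficient for DO-MoST on the outcome is reduced", the plan concludes that mediation is supported, and only then tests the indirect effect. The regressions are run "controlling for covariates, e.g., baseline value of the dependent variable". Nothing in the document provides for an indirect-effect estimate when a step fails.

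The steps apply to alcohol and medical outcomes with help use as mediator. They also apply to treatment use as outcome, with decisional conflict, motivation, commitment and self-efficacy as mediators: "Analyses will use the same general linear model approach described in the previous paragraph".

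On effect sizes, B.3.1 says "we expect to observe at least a medium effect size (.50) between the UC and DO-MoST groups in AUD help initiation and duration" and extends this to alcohol use outcomes. It gives no figure for medical outcomes, although B.3.8 says "The SF-12 will yield the primary outcome reflecting overall physical health status".

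**The concern.** An indirect effect can exist without a significant total effect, so a failed step does not show that mediation is absent. Under the plan, the question of why DO-MoST works can end with nothing reported. When an estimate is reported, it has been selected for significance and is biased upward. The order is also awkward, because mediation is declared supported before the quantity that defines it has been tested.

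What is at stake is the completeness and honesty of a secondary analysis. The comparisons behind the three primary hypotheses do not pass through these steps.

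**Working it through.** **The plan's own figure.** No power or sample size is given for the mediation analysis. B.3.1 gives 156 patients (78 per arm) for an effect of 0.50, without alpha, power or attrition rate. Assuming two-sided 5% and 80% power, 63 per arm (126 in all) are needed, and 126/0.80 = 157.5, close to 156.

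**Inputs from the documents.** Effect 0.50 for help use and alcohol outcomes (B.3.1); 78 per arm recruited. A.7 reports of the prior trial: "The 1-year follow-up rate exceeded 80%, consistent with our other projects"; 78 × 0.80 = 62.4, taken as 62. B.3.9 targets at least 70% follow-up; 78 × 0.70 = 54.6, taken as 55.

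**Assumptions.** Continuous variables with within-arm SD 1; two-sided 5%; condition-to-mediator effect a = 0.50; mediator slope b = 0.4, so the true indirect effect is 0.50 × 0.4 = 0.20; total effect 0.50; baseline covariate correlated r = 0.5 with the outcome; no mediator-outcome confounding.

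**How often the steps fail.** Normal approximation for step 1 (total effect): z = 0.50/√(2(1 − r²)/n). For step 2 (condition to mediator): z = 0.50/√(2/n). Power = Φ(z − 1.96). At n = 78, step 1 has z = 0.50/0.1387 = 3.61 and power 95.0%; step 2 has z = 0.50/0.1601 = 3.12 and power 87.7%. The mediator-to-outcome steps almost always pass here: in the joint model b/SE is about 0.4/(√0.59/√156) = 6.5. The simulation used 8,000 trials per setting and applied the whole rule, including the final test of the indirect effect.

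| Per arm | Step 1 | Step 2 | Product | Simulated pass | Fail |
|---|---|---|---|---|---|
| 78 | 95.0% | 87.7% | 83.4% | 83.8% | 16% |
| 62 | 89.5% | 79.5% | 71.2% | 72.1% | 28% |
| 55 | 85.7% | 74.6% | 63.9% | 66.6% | 33% |

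The simulated pass rate is a little above the product because the two estimates come from the same patients and are positively correlated.

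**Weaker covariate.** When treatment use is the outcome, its baseline value can explain little: B.3.3 excludes patients with specialty addiction treatment or weekly mutual-help attendance in the prior 60 days. With r = 0, step 1 has the same power as step 2. The products are 0.877² = 77.0%, 0.795² = 63.2% and 0.746² = 55.7%. Simulated failure is about 23%, 36% and 44%.

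**Smaller total effect.** At 0.35 SD (an illustration, not a planned value; slope 0.3 to 0.4, r = 0.5) the rule passes in 64–65%, 50–53% and 42–46% of trials, so it fails in 35–36%, 47–50% and 54–58%.

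**Bias among estimates that pass.** Selecting on a significant positive a-path gives a mean of about 0.50 + s·φ(z − 1.96)/Φ(z − 1.96), with s = √(2/n).
- n = 78: 0.50 + 0.160 × 0.203/0.877 = 0.537; times 0.4 = 0.215.
- n = 62: 0.50 + 0.180 × 0.284/0.795 = 0.564; times 0.4 = 0.226.
- n = 55: 0.50 + 0.191 × 0.320/0.746 = 0.582; times 0.4 = 0.233.

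Simulated means at 78, 62 and 55 per arm:
- all trials: 0.201, 0.200, 0.201
- total-effect condition alone: 0.204, 0.207, 0.211
- significant paths alone: 0.216, 0.227, 0.235
- full rule: 0.218, 0.229, 0.237

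Most of the bias comes from requiring significant paths, so dropping only the total-effect step would not remove it.

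**Chance of claiming mediation, plan v fix.** The fix allows the claim only if the indirect-effect and total-effect intervals both exclude zero. At 0.50 SD: 83.8 v 84.5% (+0.7), 72.1 v 73.2% (+1.1) and 66.6 v 67.8% (+1.2).

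**Confounding only.** Suppose there is no mediation and no total effect, condition still moves the mediator by 0.50 SD, and a within-arm mediator-outcome correlation of 0.3 is all confounding. The indirect-effect interval alone excludes zero in 87%, 77% and 71% of trials. False claims are 2.4%, 2.1% and 2.4% under the plan, and 4.1%, 3.3% and 3.5% under the fix.

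**The case against.** The total-effect step suits the stated question. B.3.11 asks for the reasons DO-MoST is effective, which presupposes that it is. Causal steps followed by a test of the indirect effect is a recognised method, and the analysis is secondary. The fix adds about 1 point to the chance of a true claim and 1 to 2 points to false claims under pure confounding. Estimates among claimed cases stay inflated (0.218, 0.227 and 0.234 in a separate simulation). The path sizes are assumed. All of this stands, and it is why the fix keeps the total effect as a condition on the claim.

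A reader might infer that the steps waste a great deal of power. If the whole effect ran through the mediator (total 0.20 SD), the plan's rule would succeed in 28% of trials at 78 per arm, against 88% for an interval taken alone. The documents do not support that reading. They give no such effect size, and the interval alone is not a sound rule for claiming mediation, as the confounding runs show. In those trials the fix supplies an estimate, not a claim.

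A reader might also infer that any loss is small wherever 0.50 SD is planned. That relies on a useful baseline covariate, which B.3.3 makes doubtful for treatment use.

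What survives is the reporting point: no estimate when a step fails, and a selected one when none does.

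**Conclusion.** The point holds as a low-cost improvement that the sponsor could adopt, not as an error. Under the stated assumptions the planned analysis gives no indirect-effect estimate in roughly one trial in six with everyone followed, and in one in three at the 70% follow-up target. It fails more often when the covariate is weaker or the total effect is smaller. For medical outcomes the rate cannot be fixed, because no effect size is given. Surviving estimates are too large by about 0.02 to 0.04 on a true 0.20.

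The figures rest on assumed paths and continuous variables; binary outcomes and mediators, such as abstinence and help initiation, were not simulated. The unbiased mean over all trials holds only without mediator-outcome confounding.

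**What to change.** In B.3.12, for each named mediator:
- Report the indirect effect with a bootstrap 95% confidence interval whatever the significance of any step, beside the total and direct effects with their intervals, using the planned covariates.
- State the scale for binary outcomes or mediators, for example the risk difference.
- Label the analysis exploratory.
- Add a sensitivity analysis for mediator-outcome confounding, such as the residual correlation at which the indirect effect reaches zero.
- Do not claim that mediation explains DO-MoST's effectiveness when the total-effect interval includes zero.

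The cost is SAP wording, a bootstrap and one sensitivity analysis on data already collected. The real downside is that help use is not randomised, so a reported interval may reflect confounding. Neither rule protects much once a direct effect exists: with a direct effect of 0.50 SD, no mediation and a confounded correlation of 0.2 to 0.3, mediation is wrongly found in 67–83% of trials under the plan and 71–87% with the interval alone at 78 per arm. The sensitivity analysis and the exploratory label are therefore part of the fix, not optional additions.
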